11.2.1.1 Adverse Event Overview

The number and percentage of subjects experiencing TEAEs will be summarized for the following AE categories:

- Any AE

- Any AE with a Reasonable Possibility of being related to study drug by the investigator
- Any severe AE
- Any serious AE
- Any serious AE with a Reasonable Possibility of being related to study drug by the investigator
- Any AE leading to discontinuation of study drug
- Any AE of special interest
- Any AE Leading to Death
- Any Deaths

Additional AEs may be considered for tabulation/summary based on recommendations for Clinical and Safety as deemed appropriate. Any event with an unknown severity will be considered as severe and any AE with an unknown relationship will be considered as drug-related.

11.2.1.2 Adverse Events by System Organ Class and Preferred Term

TEAEs will be summarized and presented using primary Medical Dictionary for Regulatory Activities (MedDRA version 16.1 or later version) system organ classes (SOCs) and preferred terms (PTs). The SOCs will be presented in alphabetical order, and the PTs will be presented in alphabetical order within each SOC.

A subject who reports more than 1 AE in different SOCs will be counted only once in the overall total. A subject who reports more than 1 AE in different PTs, which are in the same SOC, will be counted only once in the SOC total. A subject who reports more than 1 AE with the same PT will be counted only once for that PT using the most extreme incident (i.e., most severe for the severity tables and most related for the relationship tables).

11.2.1.3 Adverse Events by Maximum Severity

TEAEs will also be summarized by maximum severity. If a subject has an adverse event with unknown severity, then the subject will be counted in the severity category of "unknown," even if the subject has another occurrence of the same event with a severity present. The only exception is if the subject has another occurrence of the same adverse event with the most extreme severity "Severe." In this case, the subject will be counted under the "Severe" category.

11.2.1.4 Adverse Events by Maximum Relationship

TEAEs will also be summarized by maximum relationship to study drug, as assessed by the investigator. If a subject has an adverse event with unknown relationship, then the subject will be counted in the relationship category of "unknown," even if the subject has another occurrence of the same event with a relationship present. The only exception is if the subject has another occurrence of the same adverse event with a relationship assessment of "Reasonable Possibility." In this case, the subject will be counted under the "Reasonable Possibility" category.

11.2.1.5 Adverse Events by "Reasonable Possibility" of Being Related to Study Drug

TEAEs will also be summarized by relationship defined by "Reasonable Possibility" of being related to study drug, as assessed by the investigator. If a subject has an AE with an unknown relationship, then the subject will be counted in as with "Reasonable Possibility."

11.2.1.6 Serious Adverse Events (Including Deaths) and Adverse Events Leading to Study Drug Discontinuation

All serious adverse events (SAEs), deaths, and adverse events leading to discontinuation of study drug will be listed. The number and percentage of subjects experiencing SAEs (including deaths) and adverse events leading to discontinuation of study drug will be tabulated according to the primary MedDRA SOC and MedDRA PT.

11.2.1.7 Adverse Events of Special Interests

The Adverse Events of Special Interests (AESI) categories following the most updated PSAP will be summarized and presented using primary MedDRA system organ classes (SOCs) and preferred terms (PTs).

11.2.1.8 Adverse Events by 100 Patient Years

TEAEs will be summarized by event rate per 100 patient years, defined as

$$100 \times \frac{\text{Number of TEAEs}}{\text{Total Patient Years}},$$

where total patient years is defined as the sum of the study drug exposure of all subjects normalized by 365.25, and rounded to one decimal place.

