### **Adverse Events**

AEs will be assessed at every study visit from the first dose of study medication through to Week 24 study visit, and during the 70-day safety phone call after the last dose of ADA (or until the subject begins use of commercially available ADA, whichever comes first). In addition, all serious adverse events (SAEs) will be captured from the time the subject signs the Informed Consent Form through study completion or Premature Discontinuation and at the 70-day safety follow-up. Any new AEs/SAEs reported during the 70-day follow-up period should be submitted to AbbVie. The 70-day safety follow-up phone call

will be recorded in source documents only and confirmation of the contact will be faxed to AbbVie (Refer to Section [5.4.1](#) and [Appendix G](#) for additional information).

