### **6.1.4 Adverse Event Collection Period**

[figure not shown]
All AE reported from the time of study drugs administration until 70 days following discontinuation of study drugs administration have elapsed will be collected, whether solicited or spontaneously reported by the subject. In addition, SAEs and protocol related

non-serious AEs will be collected from the time the subject signed the study-specific informed consent. AE information will be collected and recorded on the appropriate eCRF.

Subjects will be contacted approximately 70 days following study drug (ADA) discontinuation for an assessment of any new or ongoing AEs, except those subjects that continue on ADA therapy after the end of study participation. These subjects are not required to complete the 70-day follow-up and any new AEs should be reported through the mechanism used for all post-marketing AEs.

AE information will be collected as shown in Figure 2.

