**8.1.5 Statistical Analysis of Safety**

All AEs, SAEs, and AEs leading to discontinuation will be collected during the study and up to 70 days after the last dose of ADA. Safety analyses will be carried out using the Safety Population. A treatment-emergent AE is defined as an event with onset or worsening after the first dose of study drugs (ADA + MTX) and within 70 days after the last dose of ADA. The number and percent of subjects experiencing treatment-emergent AEs will be tabulated using the Medical Dictionary for Drug Regulatory Activities (MedDRA®) system organ class and preferred term. Summaries (including percentages and event per 100 patient-years) of SAEs, deaths and AEs leading to discontinuation from the study will be provided as well.

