**Please contact all Subjects 70 days following last study drug injection (ADA)**

---

Date of Call/Visit: \_\_\_\_\_

- Call not needed as subject is continuing on commercial adalimumab.
- Lost to Follow-Up (Please check this box if subject was not willing to provide any follow-up information or you were unable to speak to the subject following at least one attempt).
- No Events Reported
- AE/SAE Reported

List any Adverse Events (AE) and/or Serious Adverse Events (SAE) that occurred since the subject was last seen in clinic for this study. Please document all adverse events on a 500 AE CRF in the EDC system. (Please report all SAEs to AbbVie within 24 hours of being made aware of the event). **In addition, please note stop dates to any adverse events that were ongoing at the last study visit.**

---

---

---

---

---

---

---

---

**Please fax this form to AbbVie at** [REDACTED]

**Appendix H. Adalimumab injection instructions****Subject Injection Instructions****0.8 mL dose****(Administered as a single dose Pen or pre-filled syringe)****Protocol W14-406****Tables of Contents**

Dosing Schedule

General Information

Injection Procedures

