9.0 Study Drug Exposure and Compliance

Summary of study drug exposure and compliance will be provided.

The study drug exposure (days) will be summarized with the mean, standard deviation, minimum, first quartile, median, third quartile and maximum, for ADA and for MTX. Study drug exposure will be summarized as follows.

Study Drug Exposure (in Days) for ADA:

- Date of last study ADA injection – Date of first study ADA injection + 14 days.

Study Drug Exposure (in Days) for MTX:

- Date of last dose of MTX – Date of first dose of MTX + 7 days.

Compliance (%), which is defined as the number of injections received divided by the number of injections planned for ADA, and as the doses received divided by the doses planned for MTX, during the subject's participation in the study (rounded to 0.1%), will be summarized separately. In addition, at each scheduled time point, the number of ADA

injections and MTX doses received and compliance will be summarized with frequencies and percentages.

When computing compliance at each scheduled time point, the denominator for each week will include all subjects in each analysis population who have not prematurely discontinued prior to the scheduled study drug injection. The date of prematurely discontinuation will be taken from vital sign dataset.

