11.2.1 Treatment-Emergent Adverse Events

Treatment-emergent adverse events (TEAE) are defined as following:

TEAEs are defined as any event with an onset date that is on or after the maximum date of either the first dose of study ADA or the first dose of MTX and no more than 70 days after the last study ADA injection during the study.

If an incomplete onset date is collected for an adverse event, the event will be assumed to be treatment-emergent unless there is other evidence that confirms that the event is not treatment-emergent (e.g., the event end date is prior to the study drug start date).

Adverse event data will be summarized and presented using the Medical Dictionary for Drug Regulatory Activities (MedDRA[®]) system organ class (SOCs) and preferred terms (PTs).

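### SAP 11.2.1.8 counts adverse events to 70 days after the last adalimumab dose but person-time to only 14 days, so rates per 100 patient-years can be up to a third too high in completers

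*SAP*

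**What the plan says.** The rate in SAP 11.2.1.8 is 100 times the number of TEAEs over total patient-years, "where total patient years is defined as the sum of the study drug exposure of all subjects normalized by 365.25". SAP 9.0 defines two exposures. For ADA it is "Date of last study ADA injection – Date of first study ADA injection + 14 days"; for methotrexate (MTX) it is "Date of last dose of MTX – Date of first dose of MTX + 7 days". Section 11.2.1.8 does not say which is meant.

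SAP 11.2.1 sets the event window. An event counts if its onset is on or after the later of the two first doses and "no more than 70 days after the last study ADA injection during the study".

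On follow-up, Protocol 6.1.4 says of subjects who stay on ADA: "These subjects are not required to complete the 70-day follow-up". The Appendix G call form has a matching tick-box: "Call not needed as subject is continuing on commercial adalimumab". Protocol 5.3.1 ends collection at 70 days or at the start of commercial ADA, whichever is earlier. Protocol 8.1.5 asks for "Summaries (including percentages and event per 100 patient-years) of SAEs, deaths and AEs leading to discontinuation".

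**The concern.** A rate per 100 patient-years is interpretable when events and person-time cover the same period. Here the numerator runs up to 56 days longer than the denominator (70 − 14). Late events do reach the numerator: Appendix G tells sites to enter events found at the 70-day call in the electronic data capture system.

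The error runs one way and its size is not fixed in advance. Subjects who continue ADA leave follow-up; those who stop are followed for 70 days. The reported rate therefore rises with the share who stop, even at identical underlying risk. The study has no control arm, so no between-arm comparison can cancel the error. At stake are the rates for all TEAEs, SAEs and deaths. The rate of events leading to discontinuation is hardly affected, because those events arise essentially on treatment.

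**Working it through.** The documents give no event rate or patient-year total, so there is no stated figure to reproduce. The check is direct arithmetic on the SAP's own rules.

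**Inputs**
- ADA is given at Weeks 0 to 22 (Protocol synopsis and 5.5.1), so last minus first = 22 × 7 = 154 days.
- MTX is given at Weeks 0 to 23, so last minus first = 23 × 7 = 161 days.
- Exposure adds 14 days (ADA) or 7 days (MTX), from SAP 9.0. The event window adds 70 days to the last ADA dose, from SAP 11.2.1.
- Both first doses are planned for the Baseline visit (Protocol Appendix H), so Rx Day 1 is taken as the same day for both drugs.
- The share *f* of completers followed for the full 70 days is not given. It is varied from 0 to 1. The rest are taken to start commercial ADA when the next dose falls due at Week 24.

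**One completer**
- ADA exposure: 154 + 14 = 168 days. MTX exposure: 161 + 7 = 168 days. The choice of drug makes no difference here.
- Event window: 154 + 70 = 224 days.
- Ratio if followed: 224/168 = 1.333. Counting both end days, Rx Day 1 to 225, gives 225/168 = 1.339.

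**Fifty completers**

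Denominator as planned: 50 × 168/365.25 = 23.0 patient-years. Time at risk: 50 × (168 + 56*f*)/365.25. The planned rate over the time-at-risk rate is (168 + 56*f*)/168 = 1 + *f*/3. The events are the same in both rates, so this ratio does not depend on how often they occur.

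| Share followed | Patient-years at risk | Planned rate too high by |
|---|---|---|
| 0% | 23.0 | 0% |
| 25% | 24.9 | 8% |
| 50% | 26.8 | 17% |
| 75% | 28.7 | 25% |
| 100% | 30.7 | 33% |

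**Against an on-treatment rate**

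Let *r* be the event rate in follow-up divided by that on treatment. The ratio becomes 1 + *rf*/3. The excess is 0% to 17% for *r* = 0.5 and 0% to 33% for *r* = 1.

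**Early stoppers (assumed shares)**

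A subject whose last ADA dose is at Week 8 has 56 + 14 = 70 days of exposure and a window of 56 + 70 = 126 days, a ratio of 1.8. If MTX also stops at Week 8, MTX exposure is 56 + 7 = 63 days, so here the choice of drug matters. Using ADA exposure, 50 subjects, and all stoppers followed:
- 10% stop: planned (45 × 168 + 5 × 70)/365.25 = 21.7 patient-years. At risk, 22.4 (*f* = 0) to 29.3 (*f* = 1). Excess 4% to 35%.
- 20% stop: planned (40 × 168 + 10 × 70)/365.25 = 20.3. At risk, 21.8 to 28.0. Excess 8% to 38%.

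**The case against.** The strongest reply is that little depends on these rates. Exposure is an openly stated denominator, the error overstates risk rather than hiding it, no safety tests are planned, and the main display of subject counts and percentages is untouched. Precision is also poor: with an assumed 2 SAEs in 23.0 patient-years the rate is 8.7 per 100, with an exact 95% interval of about 1.0 to 31.4, far wider than a 33% shift. This is a fair limit on importance, and it is why the point stops short of a critical defect. It does not cover the all-TEAE rate, where counts are likely to be larger, and imprecision does not excuse a systematic error.

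The 33% also requires every completer to stop ADA and be followed. Continuing is an expected option, and SAP 8.0 plans to tabulate it. That stands: the true excess among completers could be near zero, so only a range can be given.

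Cutting the rate numerator at 14 days would drop, say, a death on day 40 from the death rate that Protocol 8.1.5 requests. But 8.1.5 does not require rates to include events after the exposure period, and the death would remain in the counts and listings.

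Finally, ADA exposure starts at the first ADA dose while events count from the later first dose, and inclusive day counting adds one day. Both effects are negligible when the two drugs start together as planned.

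**Conclusion.** The concern holds. SAP 9.0, 11.2.1 and 11.2.1.8 together give a rate whose events and person-time cover different periods, and nothing else in either document aligns them. Among completers the planned rate exceeds the matched rate by 0% to 33%, according to the share followed. With 10% or 20% stopping after the Week 8 dose (assumed), the pooled excess is 4% to 35% or 8% to 38%. These figures assume dosing on schedule, both drugs started on the same day, and full 70-day follow-up of those counted as followed. The affected outputs are the rates for all TEAEs, SAEs and deaths. The plan should be corrected before SAP sign-off; no efficacy conclusion depends on it.

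**What to change.** **Simplest change.** In SAP 11.2.1.8, name ADA exposure as the denominator and count in the rate only TEAEs with onset from Rx Day 1 to the last study ADA dose + 14 days. For a completer that ends at Rx Day 155 + 14 = 169, the nominal Week 24 day in SAP Table 4. Show later events, to day 70, as counts. The cost is one sentence, using onset and dose dates already collected. Late events leave the rate but stay in the counts.

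**Alternative.** Use time at risk for both parts: Rx Day 1 to the earliest of last study ADA dose + 70 days, last contact or death, or start of commercial ADA. This needs last-contact dates and a censoring rule. Protocol 5.3.1.1 says the call "will be recorded in source documents only", although the Appendix G form has a call-date field and is faxed to the sponsor, so the date is probably recoverable. The form has no start date for commercial ADA, so subjects flagged as continuing need a stated rule, for example censoring at last study ADA dose + 14 days. For fully followed completers the reported rates would fall by 25% (168/224 = 0.75). Keep the exposure denominator for events leading to discontinuation; otherwise that rate would be understated by up to the same 25%.

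Neither option changes trial conduct.

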11.3 Analysis of Laboratory Data**11.3.1 Variables and Criteria Defining Abnormality**

Clinical laboratory tests conducted in the study are listed in the table below. Laboratory parameters will be reported using the standard international (SI) units.

Note: For urinalysis, only specific gravity and pH will be summarized.

Table 7. Clinical Laboratory Tests

Chemistry	Hematology	Urinalysis	Quantiferon TB Gold	Other
Albumin	Basophils	Blood	Quantifeton Mit. Minus NIL	ANA Pattern
Alkaline	Eosinophils	Glucose, Urine	Quantiferon NIL	Anti-ds DNA
Phosphatase	HCT	Ketones	Quantiferon TB Gold	Antinuclear
ALT	HGB	Leukocytes	Quantiferon TB minus	Antibody
AST	Lymphocytes	Nitrite	NIL	Hs-CRP
Calcium	Monocytes	pH		HBV DNA PCR
Cholesterol	Neutrophils	Protein, Urine		Taqman
Creatinine	Platelets	Specific Gravity		HCG,
Enzymatic	RBC	Urine		Quantitative
Glucose, Random, Serum	WBC	Microscopic		
Phosphate				
Potassium				
Sodium				
Total Bilirubin				
Total Protein				
Triglycerides				
Urea (BUN)				
Uric Acid				

11.3.2 Statistical Methods**11.3.2.1 Analysis for Continuous Laboratory Data**

Mean changes from baseline to post-baseline visits and to the final visit will be summarized with the baseline mean, the visit mean, change from baseline mean, standard deviation, and median.

11.3.2.2 Shift Table Analyses

The laboratory data will be categorized as low, normal, or high based on the normal ranges of the laboratory used in this study. The shift tables will tabulate the number and percentage of subjects with baseline values below/within/above the normal range versus minimum/maximum/final values below/within/above the normal range.

Shift tables for changes from baseline according to the normal range will be provided for each hematology, clinical chemistry and urinalysis (specific gravity and pH only) parameter. Shifts from baseline to the following endpoints will be considered: minimum value, maximum value and final value. Categories of "low or normal" and "high or normal" will be included at baseline in addition to the categories of "low," "normal," "high" and "missing."

11.3.2.3 Potentially Clinically Significant Laboratory Values

Frequencies and percentages of subjects with post baseline lab values that are Grade 3 or above according to the CTC toxicity criteria will be summarized. A separate listing will be provided that presents all of the subjects and values that are CTC toxicity Grade 3 or above. For each of these subjects, the whole course of the respective parameter will be listed.

Additional summaries will be presented for liver function tests including ALT or serum glutamic-pyruvic transaminase (SGPT), AST or serum glutamic-oxaloacetic transaminase (SGOT), alkaline phosphatase, and total bilirubin. Each laboratory value will be categorized as follows:

- $< 1.5 \times \text{ULN}$
- $\geq 1.5 \times \text{ULN} - < 3.0 \times \text{ULN}$
- $\geq 3.0 \times \text{ULN} - < 5.0 \times \text{ULN}$
- $\geq 5.0 \times \text{ULN} - < 8.0 \times \text{ULN}$
- $\geq 8.0 \times \text{ULN}$

where ULN is the upper normal limit.

Shift tables of baseline to the maximum values, and from baseline to final value will be presented using these five categories.

A listing of potentially clinically significant liver function laboratory values will be provided. The listing will include all subjects who met any of the following four criteria:

- ALT $\geq 2.5 \times$ ULN, or
- AST $\geq 2.5 \times$ ULN, or
- Alkaline phosphatase $\geq 2.5 \times$ ULN, or
- Total bilirubin $\geq 1.5 \times$ ULN

11.4 Analysis of Vital Signs

All analyses will be conducted for subjects in the Safety Population.

11.4.1 Variables and Criteria Defining Abnormality

The following vital sign parameters will be assessed: Systolic blood pressure [mmHg], Diastolic blood pressure [mmHg], Pulse [beats per minute], Respiratory rate [breaths per minute], Body Temperature [$^{\circ}$ C], Weight [kg]. The following table presents the Criteria for Potentially Clinically Significant Vital Sign Findings.

Table 8. Criteria for Potentially Clinically Significant Vital Sign Findings

Vital Sign	Category	Criteria for Potential Clinically Significant Vital Signs
Systolic Blood Pressure	Low	Value ≤ 90 mmHg and/or decrease ≥ 20 mmHg from baseline
	High	Value ≥ 180 mmHg and/or increase ≥ 20 mmHg from baseline
Diastolic Blood Pressure	Low	Value ≤ 50 mmHg and/or decrease ≥ 15 mmHg from baseline
	High	Value ≥ 105 mmHg and/or increase ≥ 15 mmHg from baseline
Pulse	Low	Value ≤ 50 bpm and/or decrease ≥ 15 bpm from baseline
	High	Value ≥ 120 bpm and/or increase ≥ 15 bpm from baseline

11.4.2 Statistical Methods

Mean changes from baseline to post-baseline visits and to the final visit in vital sign parameters will be summarized with the baseline mean, the visit mean, change from baseline mean, standard deviation, median.

Vital signs results satisfying the criteria for potentially clinically significant values will be identified in a listing. For each of these subjects, the whole course of the respective

parameter will be listed. The number and percentage of subjects who have at least one value meeting criteria for potentially clinically significant values will be provided for each selected vital sign parameter.

11.5 Analysis of ECG Parameters

ECG results will be listed in the data listings.

11.6 Analysis for Other Safety Variables

Not applicable.

11.7 Safety Subgroup Analyses

No safety subgroup analyses will be performed.

12.0 Special Statistical Topics

Not applicable.

13.0 List of Tables, Figures and Data Listings that Are to Be Programmed

To be provided in a separate document.

